9.9 Sample Collection and Handling

The actual dates and times of sample collection must be recorded on the laboratory requisition form.

Refer to the Time and Events Schedules for the timing and frequency of all sample collections.

Instructions for the collection, handling, and shipment of samples are found in the laboratory manual that will be provided for sample collection and handling.

10 SUBJECT COMPLETION/WITHDRAWAL

10.1 Completion

Subjects must remain in the study until the last scheduled visit followed by 16 weeks of safety and efficacy follow up to be considered as having completed participation in the study.

10.2 Discontinuation of Treatment

If a subject's study treatment must be discontinued before the end of the treatment regimen, this will not result in automatic withdrawal of the subject from the study.

Study agent administration to a subject must be permanently discontinued if any of the following occur:

1. The investigator (in consultation with the medical monitor) believes that for safety reasons (eg, adverse event) it is in the best interest of the subject to stop treatment.
2. Anaphylactic reaction resulting in bronchospasm with wheezing, or dyspnea requiring ventilatory support, or symptomatic hypotension with a greater than 40 mm Hg decrease in systolic blood pressure that occurs following a study agent administration.
3. Reaction suggestive of serum sickness occurring 1 to 14 days after study agent injection. These may be manifested by symptoms of myalgias, arthralgias, fever, rash, pruritus, facial, hand, or lip edema, dysphagia, urticaria, sore throat, and/or headache.
4. Opportunistic infection, ie, an infection by an organism that usually causes disease only in a host whose resistance is lowered (eg, *Pneumocystis jirovecii*, coccidioidomycosis, *Mycobacterium avium*).
5. TB
 - a. Active TB
 - b. Subject with latent TB who discontinues treatment for latent TB prematurely or is not compliant with treatment for latent TB
6. Malignancy, excluding nonmelanoma skin cancer.

CNTO 136 (sirukumab): Clinical Protocol CNTO136ARA3004 – Amendment 3

7. Demyelination, either central or peripheral.
8. Pregnancy during study participation.
9. Drug induced liver injury, including any one of the following:
 - a. Alanine transferase (ALT) or aspartate transferase (AST) $\geq 5 \times$ ULN but $< 8 \times$ ULN and cannot be monitored weekly for ≥ 2 weeks.
 - b. ALT or AST $\geq 8 \times$ upper limit of normal (ULN)
 - c. ALT or AST $\geq 5 \times$ ULN for 2 or more weeks
 - d. ALT or AST $\geq 3 \times$ ULN and total bilirubin $\geq 2 \times$ ULN (upper limit of normal) ($> 35\%$ direct bilirubin) (or ALT or AST $\geq 3 \times$ ULN **and** INR > 1.5 , if INR measured).

NOTE: if serum bilirubin fractionation is not immediately available, withdraw study drug for that subject if ALT or AST $\geq 3 \times$ ULN and total bilirubin $\geq 2 \times$ ULN. Serum bilirubin fractionation should be performed if testing is available. If testing is unavailable, record the presence of detectable urinary bilirubin on dipstick as indicative of direct bilirubin elevations and suggestive of liver injury.

- e. ALT or AST $\geq 3 \times$ ULN accompanied by clinical symptoms believed to be related to hepatitis or hypersensitivity such as new or worsening of fatigue, nausea, vomiting, right upper quadrant pain or tenderness, fever, or rash.

When any of the liver chemistry stopping criteria a-e is met, do the following:

- **Immediately** withdraw study agent for that subject
- Report the event to the Sponsor **within 24 hours** of learning its occurrence (see Section 12.4)
- Complete the Hepatobiliary Event Information Form and SAE form if the event also meets the criteria for an SAE. All events that meet criteria as described below **must be reported as an SAE**.
 - ALT or AST $\geq 3 \times$ ULN **and** total bilirubin $\geq 2 \times$ ULN ($> 35\%$ direct bilirubin) or
 - ALT or AST $\geq 3 \times$ ULN **and** INR > 1.5 (INR measurement is not required and the threshold value stated will not apply to patients receiving anticoagulants)
- Perform liver event follow up assessments, and monitor the subject until liver chemistries **resolve, stabilize, or return to baseline values as described below**.
- Do not restart study agent
- Make every reasonable attempt to have subjects meeting liver chemistry criteria a - e to return to clinic within 24 hours for repeat liver chemistries, liver event follow-up assessments (see below), and close monitoring.
- A specialist in hepatology consultation should be considered.

CNTO 136 (sirukumab): Clinical Protocol CNTO136ARA3004 – Amendment 3

- Make every reasonable attempt to monitor subjects twice weekly until liver chemistries (ALT, AST, alkaline phosphatase, bilirubin) resolve, stabilize or return to within baseline values. Criterion e subjects should be monitored as frequently as possible.

Make every attempt to carry out the **liver event follow up assessments** described below:

- Viral hepatitis serology (anti-Hepatitis A virus (HAV) IgM, HBsAg, anti-HBs, anti-HB core total, anti-HB core IgM, anti-HCV, HCV RNA, anti-Hepatitis E virus IgM, Epstein-Barr virus IgM and Cytomegalovirus IgM).
 - If HBsAg or anti-HB core IgM is positive, or if anti-HBc total is the only positive test, a specialist in hepatology consultation should be obtained.
 - If HBsAg is positive, perform hepatitis delta antibody assay. NOTE: if hepatitis delta antibody assay cannot be performed, it can be replaced with a PCR of hepatitis D RNA virus – as outlined in: <http://www.ncbi.nlm.nih.gov/pmc/articles/PMC1153793/>
- Blood sample for PK analysis, obtained within 24 hours of last dose. Record the date/time of the PK blood sample draw on the laboratory requisition form and the date/time of the last dose of study agent prior to blood sample draw on the CRF. If the date or time of the last dose is unclear, provide the subject's best approximation. If the date/time of the last dose cannot be approximated OR a PK sample cannot be collected in the time period indicated above, do not obtain a PK sample.
- Serum creatine phosphokinase (CPK), lactate dehydrogenase (LDH) and albumin.
- Fractionate bilirubin, if total bilirubin $\geq 2 \times$ ULN
- Obtain complete blood count with differential to assess eosinophilia
- Record the appearance or worsening of clinical symptoms of hepatitis or hypersensitivity, such as fatigue, nausea, vomiting, right upper quadrant pain or tenderness, fever, rash, or eosinophilia as relevant on the AE report form
- Record use of concomitant medications, acetaminophen, herbal remedies, other over the counter medications, or putative hepatotoxins, on the concomitant medications report form.
- Record alcohol use

The following are required for subjects that meet criteria of ALT or AST $\geq 3 \times$ ULN and bilirubin $\geq 2 \times$ ULN ($> 35\%$ direct) but are optional for subjects with other abnormal hepatobiliary chemistries as appropriate:

- Screen for other causes of liver disease: Total protein and globulins, ANA, ASMA (anti-smooth muscle antibodies), iron, TIBC, ferritin, alpha-1 anti-trypsin level, Type 1 anti-liver kidney microsomal antibodies, and quantitative total immunoglobulin G (IgG or gamma globulins). Additional testing should be performed if the following conditions are met:
 - If alkaline phosphatase $>$ ALT, AMA (anti-mitochondrial antibody) should be tested.
 - If patient is < 50 years of age, ceruloplasmin should also be tested.
 - If patient is sick enough to require hospitalization be hospitalized and is under age less than 50 years old, 24 hour urine copper should be tested.
 - Serum acetaminophen adduct HPLC assay (quantifies potential acetaminophen contribution to liver injury in subjects with definite or likely acetaminophen use in the preceding week)
 - Consider serum ethanol as clinically appropriate.
 - Liver ultrasound with consideration of further imaging (eg, CT, MRI, MRCP, ERCP, Doppler studies of hepatic vessels, etc., if indicated based on ultrasound findings or clinical situation)
10. Two confirmed consecutive absolute neutrophil counts of $< 0.5 \times 10^3/\mu\text{L}$ (SI: $< 0.5 \times 10^9$ cells/L).
 11. Two confirmed consecutive platelet counts $< 50,000/\mu\text{L}$ (SI: $< 50 \times 10^9$ cells/L).
 12. QTc > 500 msec* or uncorrected QT > 600 msec, Change from baseline: QTc > 60 msec*
*based on average QTc value of triplicate ECGs
 13. The initiation of protocol-prohibited medications. (see Section 8.2).
 14. Acute diverticulitis requiring antibiotic treatment
 15. Gastrointestinal perforation
 16. If sirukumab becomes approved in the subject's country of residence, it may no longer be offered by the Sponsor in CNTO136ARA3004. In this case, study agent administrations will be discontinued after 52 weeks of treatment for subjects who enrolled after completing participation in study CNTO136ARA3002, and after 104 weeks of treatment for subjects who enrolled after completing participation in CNTO136ARA3003. At that point the subject will have the opportunity to discuss treatment options with their treating physician.

CNTO 136 (sirukumab): Clinical Protocol CNTO136ARA3004 – Amendment 3

Subjects should not receive study agent administrations during the course of a serious infection. Discontinuation of study agent administration must be strongly considered for subjects who develop a serious infection such as sepsis or meningoenephalitis, and also should be considered for subjects who have serious infections requiring hospitalization or IV antibiotic therapy. Discontinuation of study agent administration should also be considered for severe injection-site reactions.

Subjects who discontinued study agent administration should continue participating in the study for safety and efficacy follow-up (Table 2).

10.2.1 Interruption of Study Agent Administration

Values for liver transaminase levels (AST, ALT), absolute neutrophil count (ANC), and platelet count that require study agent interruption and/or permanent discontinuation of study agent administration are listed below in Table 4.

Table 4: Values for liver transaminase levels, absolute neutrophil count, and platelet count that require study agent interruption and/or permanent discontinuation of study agent administration	
ALT or AST increased	
ALT or AST	Action
≥ 3 times the upper limit normal (≥ 3x ULN) for laboratory reference range.	Interrupt study agent administration, assess for symptoms, and repeat ALT/AST test as soon as possible using a liver chemistry kit as described in Section 9.8 Safety Evaluations below Hepatobiliary abnormalities.* May resume study agent when < 3x ULN**
Criteria for drug-induced liver injury (Section 10.2, #9)	Permanent discontinuation of study agent

Low Absolute Neutrophil Count (ANC)	
Neutrophil count	Action
0.5 to ≤ 1.0 x 10 ³ /μL (SI: 0.5 to ≤ 1.0 x 10 ⁹ cells/L)	Interrupt study agent administration, repeat ANC test as soon as possible* May resume study agent when > 1.0 x 10 ³ /μL**
< 0.5 x 10 ³ /μL (SI: < 0.5 x 10 ⁹ cells/L)	Interrupt study agent administration, repeat ANC test as soon as possible* If confirmed to be < 0.5 x 10 ³ /μL, discontinue study agent permanently (Section 10.2 #10)

Low Platelet Count	
Platelet count	Action
50,000 to ≤ 100,000/μL (SI: 50 to ≤ 100 x 10 ⁹ cells/L)	Interrupt study agent administration, repeat platelet count test as soon as possible* May resume study agent when platelet count > 100,000/μL **
< 50,000/μL (SI: < 50 x 10 ⁹ cells/L)	Interrupt study agent administration, repeat platelet count test as soon as possible* If confirmed to be < 50,000/μL, discontinue study agent permanently (Section 10.2 #11)
* Retesting should be done by Central laboratory	
** In case more than 3 subsequent injections are missed, and the PI wishes to resume study agent, please contact the Medical Monitor.	

10.3 Withdrawal from the Study

A subject will be withdrawn from the study for any of the following reasons:

- Lost to follow-up
- Withdrawal of consent
- Death

If a subject discontinues study agent administration before the end of the study, follow-up assessments should be obtained as per the Time and Events Schedule described in [Table 2](#).

If a subject is lost to follow-up, every reasonable effort must be made by the study site personnel to contact the subject and determine the reason for discontinuation/withdrawal. The measures taken to follow up must be documented.

When a subject withdraws before completing the study, the reason for withdrawal is to be documented in the CRF and in the source document. Study agent assigned to the withdrawn subject may not be assigned to another subject. Subjects who withdraw will not be replaced.

Withdrawal from Pharmacodynamic Research

The subject may withdraw consent for pharmacodynamics research while remaining in the clinical study. In such a case, any stored samples will be destroyed upon communication from the site to the Sponsor. No pharmacogenetics testing will be conducted on these samples. This does not include those samples specifically collected for pharmacogenetic analysis for which separate optional consent was obtained.

Withdrawal from Pharmacogenetics Research

The subject may withdraw consent for pharmacogenetics research while remaining in the clinical study. In such a case, any DNA extracted from the subject's blood will be destroyed upon communication from the site to the Sponsor. If requested, the investigator will receive written confirmation from the Sponsor that the sample has been destroyed.

11 STATISTICAL METHODS

Statistical analysis will be done by the Sponsor or under the authority of the Sponsor. Descriptive statistics (eg, mean, median, standard deviation, interquartile range, minimum, and maximum) will be used to summarize continuous variables. Counts and percentages will be used to summarize categorical variables.

Subjects will continue to receive the same treatment regimen administered in studies CNTO136ARA3002 and CNTO136ARA3003 at Weeks 104 and 52, respectively:

- Group 1: Sirukumab 100 mg SC q2 weeks
- Group 2: Sirukumab 50 mg SC q4 weeks

CNTO 136 (sirukumab): Clinical Protocol CNTO136ARA3004 – Amendment 3

After the study becomes open-label, subjects treated with SC sirukumab 100 mg q2 weeks will be offered the option to reduce the sirukumab dose to 50 mg q4 weeks at the investigator's discretion. This decision can be made at the subject's first or second major resupply visit (up until approximately 7 months) after implementation of Amendment 3 at the study site.

Since the treatment groups are not randomly assigned in this study, no formal hypothesis testing is planned. The efficacy, safety, and PK/PD/immunogenicity analyses will be performed separately for subjects who complete studies CNTO136ARA3002 and CNTO136ARA3003. The analyses will include all subjects enrolled by study and by treatment group above.

Additional data releases or locks may occur periodically as needed. The analyses based on these data releases or locks intend to integrate data from CNTO136ARA3002 and CNTO136ARA3003 with this study for the long-term PK, immunogenicity, safety and efficacy data of all subjects enrolled in these studies. A separate SAP for integration will be developed to specify the analyses and data handling rules.

An independent DMC will monitor the safety of the blinded portion of the study in unblinded fashion on a regular basis and whenever deemed necessary. Additional details are provided in Section 11.10.

11.1 Subject Information

Unless otherwise stated, in general, all subjects who enrolled this study will be included in analyses. Analyses will be performed based on the treatment groups defined in Section 11.

11.2 Efficacy and Safety Analyses

Baseline value in efficacy and safety is defined as the baseline value of study CNTO136ARA3002 or CNTO136ARA3003. No missing data imputation will be used.

11.2.1 Primary Endpoint

The number of subjects with each of the following long-term safety events through the end of study: cardiovascular SAEs, malignancies, serious infections, and gastrointestinal perforations will be summarized.

Serious cardiovascular events adjudicated by the CEC will be summarized by treatment group.

No hypothesis testing will be performed.

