The maximum duration of participation in this study is 208 weeks, followed by approximately 16 weeks of safety and efficacy follow-up after the administration of the final study agent injection of sirukumab. Only 1 database lock (DBL; at the end of the study) is planned. Additional data releases or locks may occur as needed. The study will end with the last visit for the last subject participating in the study.

CNTO 136 (sirukumab): Clinical Protocol CNTO136ARA3004 – Amendment 3

Study treatment will remain blinded in CNTO136ARA3004 until the following 3 conditions have been met: the Week 52 DBL occurs in study CNTO136ARA3002, the Week 24 DBL occurs in study CNTO136ARA3003, and the last AI usability substudy subject completes the Week 16 visit or terminates from the study. Thereafter study CNTO136ARA3004 will become open-label and placebo injections will be discontinued in the SC sirukumab 50 mg treatment group. Once study CNTO136ARA3004 becomes open-label, study subjects will receive open-label study agent through IVRS/IWRS. However, when this study becomes open-label, any subjects who still remain in studies CNTO136ARA3002 and CNTO136ARA3003 due to staggered enrollment will continue to receive blinded treatment until they complete participation in those studies.

Protocol waivers or exemptions are not allowed with the exception of immediate safety concerns. Therefore, adherence to the study design requirements, including those specified in the Time and Events Schedules are essential and required for study conduct.

Subject safety will be monitored through the end of the study as delineated in the Time and Events Schedules.

The primary endpoint is the number of subjects with each of the following long-term safety events through the end of the study: cardiovascular (CV) SAEs, malignancies, serious infections, and gastrointestinal perforations.

The major secondary endpoint is laboratory parameters of interest (neutrophils, platelets, hepatobiliary parameters, and lipid parameters).

Serum samples will be collected for the evaluation of sirukumab PK and antibodies to sirukumab. Other samples to be collected include serum and whole blood RNA for the evaluation of inflammation-associated proteins and other analytes. These samples will be used to better understand the biology of RA, to analyze differences between responders and non-responders, and to assess loss of response.

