3.2.3 Study Phases and Duration of Treatment

There will be 3 phases of this LTE study: Blinded active treatment, open-label treatment, and safety and efficacy follow-up.

CNTO 136 (sirukumab): Clinical Protocol CNTO136ARA3004 – Amendment 3

As described in Section 3.2.2, the blinded active treatment phase will continue until following 3 conditions have been met: the Week 52 DBL occurs in study CNTO136ARA3002, the Week 24 DBL occurs in study CNTO136ARA3003, and the last AI usability substudy subject completes the Week 16 visit or terminates from the study.

The open-label treatment phase of the study will begin after those 3 conditions have been met, and will continue through the last scheduled dose for all subjects. The safety and efficacy follow-up will include approximately 16 weeks of study evaluations following the last administration of study agent, including follow-up for patients who discontinued study treatment prior to their last scheduled dose. The safety and efficacy follow-up allows for monitoring of the subject for a period of equivalent to at least 5 times the half-life of sirukumab.

The maximum duration of the study is expected to be 156 weeks for subjects enrolling after participation in study CNTO136ARA3002 and 208 weeks for subjects enrolling after participation in study CNTO136ARA3003, followed by approximately 16 weeks of safety and efficacy follow-up after the administration of the final study agent injection of sirukumab.

After a minimum of 1 year treatment in CNTO136ARA3004 for subjects from study CNTO136ARA3002, or a minimum of 2 years of treatment in CNTO136ARA3004 for subjects from CNTO136ARA3003, and after sirukumab is approved for the treatment of RA in the subject's country of residence, the Sponsor may no longer offer study treatment in CNTO136ARA3004 for those specific subjects. At that point the subject will have the opportunity to discuss treatment options with their treating physician.

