11.8 Safety Analyses

Adverse Events

The verbatim terms used in the eCRF by investigators to identify AEs will be coded using the MedDRA dictionary. All reported AEs with onset during the treatment phase (ie, treatment-emergent AEs and AEs that have worsened since baseline) will be included in the analysis. For each AE, the percentage of subjects who experience at least 1 occurrence of the given event will be summarized by treatment group. Other safety analyses include the proportion of subjects with infections, SAE, AE leading to discontinuation.

Summaries, listings, datasets, or subject narratives may be provided, as appropriate, for those subjects who die, who discontinue treatment due to an AE, or who experience a severe or a serious adverse event (SAE).

Additional analyses will be performed for the number of subjects with cardiovascular SAEs by cardiovascular type and the number of subjects with malignancies by malignancy type (eg, lymphoma, nonmelanoma skin cancers, and other malignancies).

Clinical Laboratory Tests

Laboratory data will be summarized by type of laboratory test. NCI-CTCAE grades will be used in the summary of laboratory data. For some laboratory data, which are not covered in the NCI-CTCAE grading criteria, shift tables and/or other abnormal cutoff levels may be used for summaries. Descriptive statistics will be calculated for selected laboratory analyte at baseline and at each scheduled time point. A listing of subjects with post-baseline abnormal laboratory results based on NCI-CTCAE grades will also be provided.

Vital Signs

The proportion of subjects with markedly abnormal post-baseline values will be summarized.

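### The Protocol reports the primary long-term safety events only as numbers and percentages of subjects, with no person-time denominator, although length of follow-up varies within every table cell.

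*Protocol*

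**What the plan says.** The primary objective is long-term safety (Protocol 2.1). Section 3.1 states: "The primary endpoint is the number of subjects with each of the following long-term safety events through the end of the study". The events are cardiovascular SAEs, malignancies, serious infections and gastrointestinal perforations. Section 9.2.3 uses the same measure, and the analysis in Section 11.2.1 repeats it: "The number of subjects with each of the following long-term safety events through the end of study". Section 11 sets the general rule: "Counts and percentages will be used to summarize categorical variables". For adverse events, Section 11.8 says that "the percentage of subjects who experience at least 1 occurrence of the given event will be summarized by treatment group", and it breaks cardiovascular SAEs and malignancies down by type as numbers of subjects. No Protocol section names person-years, an exposure-adjusted rate or a time-to-event summary.

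Grouping is settled. Analyses are run separately by parent study, and "The analyses will include all subjects enrolled by study and by treatment group above", the groups being the regimen at entry to the extension. Section 11.1 repeats this: "Analyses will be performed based on the treatment groups defined in Section 11".

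On duration, Section 3.2.3 says that the maximum "is expected to be 156 weeks for subjects enrolling after participation in study CNTO136ARA3002 and 208 weeks" for those from CNTO136ARA3003, plus about 16 weeks of follow-up. Under Sections 9.1.4 and 10.2, subjects who stop study agent early but remain in the study have about 16 weeks of assessments after the last injection. Section 10.3 withdraws subjects who die, withdraw consent or are lost. Section 10.2 makes malignancy (other than nonmelanoma skin cancer) and gastrointestinal perforation grounds for permanent discontinuation.

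**The concern.** A percentage of subjects with an event estimates risk over a stated period only if nearly everyone is observed for that period. Here observation ends earlier for anyone who stops treatment or leaves. Two of the four primary event types also end treatment, which shortens observation for the other types in the same subject. Two cells with the same underlying hazard can therefore show different percentages, and a reader cannot recover the risk because the denominator carries no time.

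No test is planned, so this descriptive summary is the whole primary result. What is at stake is whether it can be read as an absolute long-term risk or set beside other long-term data.

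**Working it through.** **Inputs from the Protocol.** Planned treatment is D = 156 weeks (from CNTO136ARA3002) or 208 weeks (from CNTO136ARA3003), Section 3.2.3. Follow-up after the last injection is 16 weeks, Section 9.1.4. The Protocol's totals agree with each other: 104 + 156 = 52 + 208 = 260 weeks, about 5 years. It states no event count, event rate, sample size or discontinuation rate, so there is no planned figure to reproduce.

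**Assumptions, not in the documents.** Constant hazard λ of 0.5, 1, 2, 3 or 5 per 100 person-years. A share s of 10% to 40% stops at a time uniform over 0 to D weeks, unrelated to event risk, and is then followed for 16 weeks. All others complete D + 16 weeks.

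**Formulas** (52 weeks per year, λ per person-year):
- Complete follow-up: F = 1 − exp(−λ(D + 16)/52).
- Early stopper, averaged over stopping time: E = 1 − exp(−16λ/52) × [1 − exp(−λD/52)]/(λD/52).
- Ratio of the crude percentage to its value with no early stopping: R = [(1 − s)F + sE]/F.

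**Worked case**, D = 156, λ = 1 per 100 person-years, s = 40%:
- F = 1 − exp(−0.01 × 172/52) = 3.25%.
- E = 1 − 0.99693 × 0.98515 = 1.79%.
- Crude percentage = 0.6 × 3.25% + 0.4 × 1.79% = 2.67%, so R = 0.82.
- Mean scheduled follow-up = 0.6 × 172 + 0.4 × (78 + 16) = 140.8 of 172 weeks (for D = 208, 182.4 of 224).

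**Results, R:**

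| λ per 100 PY | D = 156, s = 10% | D = 156, s = 40% | D = 208, s = 10% | D = 208, s = 40% |
|---|---|---|---|---|
| 0.5 | 0.955 | 0.819 | 0.954 | 0.815 |
| 1 | 0.955 | 0.820 | 0.954 | 0.816 |
| 2 | 0.955 | 0.821 | 0.954 | 0.817 |
| 3 | 0.956 | 0.822 | 0.955 | 0.819 |
| 5 | 0.956 | 0.825 | 0.955 | 0.822 |

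The relative fall is 4.4% to 4.6% when 10% stop and 17.5% to 18.5% when 40% stop, so about 4% to 19% overall. It depends mainly on how many stop and hardly on the hazard. Under these assumptions, first events divided by person-years at risk has expectation λ in every cell of the table, so the rate is unaffected.

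**Precision.** In an assumed 1,000 person-years, exact Poisson 95% intervals per 100 person-years are 0 to 0.37 for 0 events and 0.02 to 0.72 for 2 events.

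**The case against.** - **The SAP may already contain this.** Its text was not available, and exposure-adjusted rates are detail that a SAP can hold. Section 11 also promises a separate SAP for the integrated long-term analyses. This stands as a limit: the absence can be claimed for the Protocol only.
- **The effect is modest and assumed.** Also true. With a relative half-width of roughly 1.96/√n, sampling error exceeds a 19% shortfall until a cell has about 106 events ((1.96/0.19)² ≈ 106). For rare events, noise would probably dominate. The shortfall is systematic, however, and without total person-years a reader cannot judge it.
- **The 16-week truncation is not universal.** Section 9.8 asks subjects stopped for non-compliance with latent-TB treatment to return for all later scheduled visits, while cross-referring to Section 10.2. Withdrawn subjects may have less than 16 weeks. The statement therefore applies to subjects who stop early, remain in the study and follow the general rule.
- **Person-time does not cure informative stopping.** Correct. Events that force discontinuation also affect few subjects: at 1 per 100 person-years, about 3% over 172 weeks.

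A reader might also infer that the 156- against 208-week difference distorts the results. At equal hazards the percentages would differ 1.27- to 1.33-fold between parent studies (224 against 172 weeks, or 208 against 156). But Section 11 analyses the parent studies separately, so this is not a planned contrast. It matters only to someone who compares the two sets of tables.

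A larger distortion might be inferred from treatment ending at 52 or 104 weeks. That requires approval in the subject's country and a Sponsor decision, and no planned table contrasts those durations.

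**Conclusion.** The point holds for the Protocol, at modest size. The stated summary has no time in its denominator while follow-up varies within each cell, so the crude percentage understates risk over the planned period to a degree that depends on discontinuation. The shortfall of about 4% to 19% rests on assumed constant hazards of 0.5 to 5 per 100 person-years and on 10% to 40% stopping at uniform times, independently of risk.

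A reader might infer a biased comparison between doses. The documents do not support that: planned duration is the same for both regimens, grouping by regimen at entry is fixed, and nothing shows that stopping differs by dose. Nor is any test invalidated, because none is planned.

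Separately, Section 11.8 limits its general tables to "All reported AEs with onset during the treatment phase", while Section 3.2.3 lists follow-up as its own phase. Whether those tables include the 16 weeks is a minor clarification. It does not touch the primary window, which runs through the end of the study.

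**What to change.** In Section 11.2.1 keep the numbers of subjects and add, for each event type by parent study and treatment group at entry to the extension:

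1. Total person-years at risk and subjects with a first event in this study per 100 person-years, with exact Poisson 95% confidence intervals, counting time from Week 0 of the extension to first event or last study visit.
2. Cumulative incidence at Weeks 52, 104 and 156 (and 208 for subjects from CNTO136ARA3003) by the Aalen-Johansen estimator with death as a competing event. This also serves as a check on the constant-hazard reading of the rate.

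If the SAP or the integration SAP already provides these, cite it in Section 11.2.1 instead. In Section 11.8, add a sentence saying whether the general adverse event tables include the 16-week follow-up.

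The cost is Protocol wording and a little programming from dates already collected, with no new data and no test. The downsides should be stated: the rate assumes a roughly constant hazard, neither summary removes informative stopping, and intervals for rare events will be wide.
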